7. STUDY PROCEDURES AND SCHEDULE

7.1 STUDY PROCEDURES/EVALUATIONS

7.1.1 STUDY SPECIFIC PROCEDURES

Collection of Adverse Events Data

Data regarding AEs will be collected in this study. As this is an extension trial, AE collection will continue from the parent study, ongoing AEs at the end of the parent study will continue to be monitored, and new AEs that occur during this study will be recorded. Changes to ongoing

AEs that occur after the parent-study EOS visit will not be recorded in the parent study. AEs will be assessed through the Termination Visit.

Each subject will be observed and queried by the Investigator or designee at each study visit for any continuing AEs or new AEs since the previous visit. The subject may be asked to return to the site for an unscheduled visit if an AE occurs between study visits, and if, in the opinion of the Investigator, the AE requires a study visit for full evaluation. The following information will be recorded within the eCRF for each AE: Description of the event, date of onset and resolution, and severity as assessed by the Investigator according to the Clinical Data Interchange Standards Consortium (CDISC) Severity/Intensity Scale for Adverse Events (AESEV) ([Table 1](#)), causal relationship to study medication, outcome, and any action taken.

In this protocol, signs and symptoms of exacerbation or worsening of target knee OA will be captured in the context of efficacy assessments and recorded on specific pages of the eCRF. Anticipated fluctuations or anticipated deterioration (in the opinion of the Investigator) of the underlying disease (target knee OA) will not be considered as AEs nor captured on the AE eCRF.

Whenever possible, it is preferable to record a diagnosis as the AE term rather than a series of symptoms relating to a diagnosis. Fluctuations of pre-existing conditions that do not represent a clinically significant exacerbation or worsening need not be considered AEs.

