7.3 STUDY SCHEDULE

7.3.1 SCREENING/ENROLLMENT

Visit 1E

Visit 1E should occur at the subject's parent-study EOS visit, with a window of + 6 weeks.

Collection of NSAID/acetaminophen usage, physical and knee examination, weight measurement, vital sign measurements, and venipuncture and collection of samples for clinical laboratory tests and biomarker analysis will be performed at the parent-study Week 56 (EOS) visit and therefore do not need to be repeated at Visit 1E.

The Investigator or designee must explain the nature of the study protocol and associated risks to the potential study participant. The potential participant must be allowed to review the study information and to ask questions before being asked to sign and date the ICF. Written informed consent must be provided, signed, and dated by the potential study participant prior to initiation of any screening evaluations or other study-related procedures. The signature, date, and the name of the individual at the site who obtained the informed consent will be recorded. Subjects will retain the same subject number as assigned in the parent study.

Subjects who sign the ICF at Visit 1E will be considered consented. For WOCBP, a urine-based pregnancy test will then be performed.

After the subject is deemed eligible for the study based on inclusion/exclusion criteria, the following procedures and assessments will be performed at Visit 1E:

- PASS assessment
- Pain NRS assessment
- Collection of AE and concomitant procedures/therapies/medication data
- IA injection of study medication by the Unblinded Investigator (injector) into the target knee; **the target knee must be the same as the knee injected in the parent study.**

Investigators will maintain a confidential log of all subjects who have been screened for participation in the study whether or not the subject was eligible for study participation.

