8.3 TIME PERIOD AND FREQUENCY FOR EVENT ASSESSMENT AND FOLLOW-UP

The reporting period for AEs starts immediately following the parent-study EOS visit and ends after the final study visit.

AEs will be followed until the subject's last visit or resolution, whichever comes first. For subjects who discontinue from the study within 30 days of their last study injection, AEs that are ongoing at the subject's last visit will be followed for 30 days after administration of the last dose or until resolution, whichever comes first. Resolution is defined as the return to baseline status or stabilization of the condition. SAEs and selected AEs identified by the Investigator or the Sponsor to warrant further follow-up that are ongoing at a subject's last visit will be followed until resolution.

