10.1 Adverse Events

Data regarding AEs will be collected in this study. As this is an extension trial, AE collection will continue from the parent study, ongoing AEs at the end of the parent study will continue to be monitored, and new AEs that occur during this study will be recorded. Changes to ongoing AEs that occur after the parent-study EOS visit will not be recorded in the parent study. AEs will be assessed through the Termination Visit. AEs will be presented in summary tables depicting the number and percent of unique subjects experiencing each AE and the number of AEs by the following analysis periods: (1) AEs that started prior to a Second OA-07 Injection (end of the single-blind, placebo-controlled period of the study; including all AEs for subjects who only received the First OA-07 Injection to End of Study, EOS), (2) on or after Second OA-07 Injection to prior to Third OA-07 Injection (including all AEs for subjects who received the Second OA-07 Injection to EOS), and (3) on or after Third OA-07 Injection to EOS. The following summaries will be provided:

- All AEs and all SAEs by severity and relationship to study product
- AEs by highest degree of seriousness, severity, and relationship to study drug
- AEs by MedDRA system organ class and preferred term
- SAEs sorted by preferred term incidence
- AEs with incidence of greater than 2% in the active treatment group sorted by preferred term incidence
- Target-knee-related AEs and SAEs sorted by preferred term incidence
- AEs leading to study withdrawal, discontinuation of study drug, or death
- SAEs in subjects diagnosed with COVID-19

If an AE start or end date is incomplete, it will be imputed in a way that assumes maximum exposure time (see table in [Appendix 3 – Partial Date Imputation](#)). Separate subject-level listings will be provided for all AEs and all SAEs.

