15.3 Appendix 3 – Partial Date Imputation

Partial Date Availability	Impute Start Date		Impute End Date	
Year (YYYY)	Prior to first OA-07 injection year	YYYY-12-31	Prior to end of study year	YYYY-12-31
	Same as first OA-07 injection year	Injection Date	Same as end of study year	End of Study Date
	After first OA-07 injection year	YYYY-01-01	After end of study year	YYYY-01-01
Year and Month (YYYY-MM)	Prior to first OA-07 injection year and month	YYYY-MM-[DD, last day of month]	Prior to end of study year and month	YYYY-MM-[DD, last day of month]
	Same as first OA-07 injection year and month	Injection Date	Same as end of study year and month	End of Study Date
	After first OA-07 injection year and month	YYYY-MM-01	After end of study year and month	YYYY-MM-01
Ongoing or unknown status at end of study (e.g., no end date and unknown whether ongoing)	Not Applicable		End of Study Date	
Additional Considerations	If the end date is not missing, and the imputed start date is after the end date, the start date will be set equal to the end date.		If the imputed end date is before the start date, then the imputed end date will be set equal to the start date.	

Signature Page for VV-TMF-221629 v1.0

Reason for signing: Approved	Name: [name] Role: Associate Director, Biostatistics Date of signature: 03-Nov-2023 19:05:16 GMT+0000
Reason for signing: Approved	Name: [name] Role: Chief Medical Officer Date of signature: 03-Nov-2023 19:06:55 GMT+0000
Reason for signing: Approved	Name: [name] Role: Vice President, Biometrics Date of signature: 03-Nov-2023 19:14:51 GMT+0000

Signature Page for VV-TMF-221629 v1.0

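### AE analysis period 1 in SAP 10.1 has no start bound, so events that began before the first OA-07 injection meet its wording and can raise the reported second-year incidence

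*SAP*

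**What the plan says.** SAP 10.1 presents AEs in three periods:

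- Period 1: "AEs that started prior to a Second OA-07 Injection". It is described as the single-blind, placebo-controlled part of the study, and for subjects with only one OA-07 injection it runs to EOS.
- Period 2: "on or after Second OA-07 Injection to prior to Third OA-07 Injection".
- Period 3: "on or after Third OA-07 Injection to EOS".

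On collection, Protocol 8.3 states: "The reporting period for AEs starts immediately following the parent-study EOS visit and ends after the final study visit". Protocol 4.1 agrees. Protocol 7.3.1 places Visit 1E, where the first OA-07 injection is given, at the "parent-study EOS visit, with a window of + 6 weeks".

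On events that began in OA-11, Protocol 7.1.1 says that "ongoing AEs at the end of the parent study will continue to be monitored", and SAP 10.1 repeats this. Both add that changes to those events after the parent EOS visit are not recorded in the parent study.

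SAP 3.2.3, safety endpoint 1, covers AEs during the study up to the end of the placebo-controlled portion. Its end is explicit and its start is only implied. SAP Section 10 plans no formal tests for safety.

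**The concern.** The primary objective includes the safety of a second year of LOR, and period 1 is the only placebo-controlled safety period in OA-07. A reader will take its tables as what happened after the second-year injection. An event that began before that injection cannot be an effect of it. As worded, such an event would still enter the period 1 tables of incidence, severity, relationship and target-knee events, and could help carry a preferred term over the 2% reporting threshold in the active group.

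**Working it through.** **Which events meet the wording**

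1. *Onset after parent EOS, before the Visit 1E injection.* Protocol 8.3 makes these OA-07 events. They started before the second OA-07 injection, so they are in period 1. Nothing in the SAP removes them. SAP 10.4 sends pre-injection findings to medical history, but only examination findings, and it does not say which study's injection is meant.
2. *Onset in OA-11, ongoing at parent EOS.* These also started before the second OA-07 injection, so the literal rule admits them. Protocol 8.3 and SAP 3.2.3 point the other way. No section says they are tabulated and none excludes them. Appendix 3 has a row for start dates "Prior to first OA-07 injection year", but SAP 12.1 uses the same table for concomitant medications, and a date-imputation rule does not decide which events are counted.

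**Size of the gap effect**

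The documents give no AE rate, so there is no planned figure to reproduce. From the documents: the gap g is 0 to 6 weeks (Protocol 7.3.1) and Visit 3E is 48 weeks after the Visit 1E injection (Protocol 7.3.2). Assumed: a constant hazard, a true 48-week incidence p, and the same gap g for every subject.

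- Share of observed time before injection at the maximum gap: 6/(6 + 48) = 11.1%.
- Reported incidence = 1 − (1 − p)^((48 + g)/48).

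| True p | g = 0 | g = 2 weeks | g = 6 weeks |
|---|---|---|---|
| 10% | 10.0% | 10.4% | 11.2% |
| 30% | 30.0% | 31.0% | 33.1% |
| 50% | 50.0% | 51.4% | 54.1% |

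For example, 1 − 0.7^(54/48) = 0.3305. The relative rise stays below 6/48 = 12.5%, a limit approached only for rare events. For a single term at the 2% threshold, 1 − 0.98^(54/48) = 2.25%.

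**Direction of the effect on the LOR-placebo difference**

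Assume true incidences of 40% (LOR) and 30% (placebo), a difference of 10 points.

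- *Maximum gap, each arm keeping its own hazard:* 1 − 0.6^(54/48) = 43.7% and 1 − 0.7^(54/48) = 33.1%. The difference widens to 10.7 points.
- *Maximum gap, both arms at the placebo hazard during the gap:* the difference is 10 × 0.7^(6/48) = 9.6 points. It narrows.
- *No gap, carried-over AEs in a share b of subjects, independent of new AEs:* incidence = 1 − (1 − p)(1 − b).

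| b, LOR / placebo | LOR | Placebo | Difference |
|---|---|---|---|
| 10% / 10% | 46.0% | 37.0% | 9.0 points |
| 10% / 5% | 46.0% | 33.5% | 12.5 points |
| 5% / 10% | 43.0% | 37.0% | 6.0 points |

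The direction depends on the assumption. SAP 4.3 keeps each subject on the parent-study treatment at Visit 1E, so events before that injection arose after the same arm's OA-11 treatment and may themselves differ by arm. The documents give no value for b, so this table shows direction and not size.

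**The case against.** The strongest reply is that collecting gap events in OA-07 is deliberate. The protocol starts AE reporting at parent EOS and its endpoint covers the whole study, so including them follows the protocol. The nominal gap is zero, since Visit 1E should fall at the parent EOS visit and 6 weeks is only the outer window. Safety is descriptive, and listings of all AEs are planned.

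Much of this stands. The events belong in the database, the 6-week figures are a ceiling, and no error rate or power is affected. It does not justify a placebo-controlled period table that mixes onsets before and after the injection when the other two periods are tied to an injection.

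Three stronger readings are tempting:

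- A reader might infer that the rule dilutes the LOR-placebo difference and so hides a safety signal. That needs the extra events to be balanced, or nearly so, between arms. The documents do not say so, and arm-specific hazards alone widen the difference.
- A reader might infer that OA-11-onset events are counted as a matter of fact. The wording permits this, but Protocol 8.3 and SAP 3.2.3 suggest otherwise. It is an ambiguity to settle.
- A reader might infer that parent-study events are double-counted. That depends on how OA-11 was reported, which these documents do not show.

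**Conclusion.** The defect holds for gap-onset events: followed as written, SAP 10.1 counts onsets before the first OA-07 injection in period 1. For OA-11-onset events the text is ambiguous and should be resolved. Including either kind can only raise the reported second-year incidence. From the gap alone, the rise ranges from nothing, when Visit 1E is on the EOS day, to about 1.2, 3.1 or 4.1 points at an assumed true incidence of 10%, 30% or 50% when every subject waits the full 6 weeks. These figures rest on a constant hazard and on assumed rates. The contribution of carried-over AEs cannot be sized, and the effect on the between-arm difference has no known direction. The point is worth correcting because it touches the primary safety objective and the correction is cheap.

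**What to change.** - In SAP 10.1, define period 1 as onset on or after the first OA-07 injection and before the second, or to EOS for subjects with only one OA-07 injection.
- Tabulate separately, by arm, (a) AEs with onset after parent EOS and before the Visit 1E injection, and (b) AEs ongoing from OA-11.
- State that events in (b) are not period 1 onsets unless recorded as worsened after the injection.
- Align safety endpoint 1 in SAP 3.2.3 and note the change in SAP Section 13.

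The cost is a date condition, one extra table and some added programming, mainly for the worsening rule, which needs severity before and after the injection. No event is lost: the separate table and the planned listings preserve the protocol's whole-study view.

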4.3 Method of Treatment Assignment and Randomization

Subjects were randomized in the SM04690-OA-11 study. Each subject maintained the same treatment assignment of LOR or placebo as in the parent study at Visit 1E (Day 1). At Visit 3E

(Week 48) and for any subsequent injections until the Termination Visit, all subjects received LOR injection(s).

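### SAP 10.1 assigns AEs to periods by start date only, so an AE that worsens or becomes serious after the crossover injection need not appear in the post-crossover period

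*SAP*

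**What the plan says.** SAP 10.1 counts subjects and events in three periods. The first ends the single-blind, placebo-controlled part and holds "AEs that started prior to a Second OA-07 Injection". The second runs "on or after Second OA-07 Injection to prior to Third OA-07 Injection", and the third begins at the third injection. Onset is the only criterion offered for placing an event. Among the planned summaries is "AEs by highest degree of seriousness, severity, and relationship to study drug"; the section does not say whether that maximum is confined to the period being tabulated.

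Protocol 7.1.1 sets out what is recorded for each AE: "Description of the event, date of onset and resolution, and severity as assessed by the Investigator", followed by causality, outcome and action taken. No date of a change in grade is listed. Protocol 8.3 governs follow-up: "AEs will be followed until the subject's last visit or resolution, whichever comes first". An event still open at Visit 3E is therefore followed across the crossover injection.

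The one rule on changes to an open event concerns the hand-over from the parent study: "Changes to ongoing AEs that occur after the parent-study EOS visit will not be recorded in the parent study". Nothing equivalent exists at the second or third OA-07 injection, and neither document defines a treatment-emergent AE.

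**The concern.** Two safety questions depend on where an event is placed. SAP 3.2.3 makes AE and SAE incidence, severity and relationship before the second OA-07 injection the first safety endpoint, and this is the only placebo-controlled AE comparison in OA-07. Protocol 4.2 justifies moving placebo subjects to LOR partly by the long-term safety information to be gained in people new to the drug.

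An existing complaint that becomes severe or serious after first LOR exposure is information of exactly that kind, and an onset-only rule can leave it out. The protocol sees the need for a fresh reference point elsewhere: Protocol 10.4.2 measures later laboratory and vital-sign changes in crossover subjects against Visit 3E. AEs get no such treatment.

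**Working it through.** No arithmetic applies. The documents give no AE rate, no count of events open at Visit 3E and no power statement for safety, so the check is a reading of the rules against one case.

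**Case.** A subject on placebo in the parent study and at Visit 1E has a mild AE that starts before Visit 3E. The subject receives LOR at Visit 3E (SAP 4.3). The AE then becomes severe or serious.

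**Step 1: period.** The start date precedes the second OA-07 injection, so SAP 10.1 puts the record in period 1, under placebo. No clause adds it to period 2.

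**Step 2: grade.** The result depends on how the site recorded the worsening. Three conventions fit the field list in Protocol 7.1.1:

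| Recording convention | Period 1 (placebo) | Period 2 (after first LOR) |
|---|---|---|
| A. One record, updated to worst grade | Severe or serious event, unless the summary is cut off at the second injection | Nothing |
| B. New record opened at worsening | Mild event | Severe or serious event |
| C. One record, grade fixed at onset | Mild event | Nothing |

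Only B shows the worsening where it happened. Under A and C it is absent from period 2, and under A it is also credited to placebo.

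**Step 3: is B required?** Protocol 8.1.1 says an AE may include an exacerbation of a pre-existing condition, so a site could open a new record. The text is permissive, and it is not applied to an AE already open on the eCRF. Protocol 14.1 refers to eCRF Completion Guidelines, which are not among the documents and might settle the matter.

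**Step 4: the LOR arm.** Take the same history in a subject on LOR throughout. Under A the event lands in period 1 under LOR. The period is wrong but the treatment is right. Convention A therefore adds late worsenings to both arms of period 1 and removes them from both groups in period 2.

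**The case against.** The strongest reply is that the rule is silent rather than wrong, and that stronger conclusions do not follow. Four such conclusions are tempting.

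- *Events are counted at their worst grade in the placebo period.* This needs convention A, which neither document states. The highest-degree summary more naturally means that a subject with several AEs in a period is shown once, at the highest category. SAP 3.2.3 also limits the endpoint to the time before the second injection.
- *The error favours LOR in the controlled comparison.* Step 4 shows that both arms of period 1 would gain events. A net shift towards LOR would need more worsening after first than after repeat exposure, and nothing in the documents supports that.
- *AEs carried over from the parent study are lost in the same way.* Period 1 has no lower bound on onset. Read literally, it includes an event that began in the parent study and worsened after Visit 1E.
- *The number affected can be estimated.* It cannot. The documents have no source for either the number of open events or the share that worsen. Anticipated deterioration of target-knee OA is not recorded as an AE at all (Protocol 7.1.1), which removes one obvious source.

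Other mitigating facts are fair. Safety analysis is descriptive (SAP 10). All AEs and SAEs are listed by subject. An event that becomes serious triggers a report within 24 hours of site awareness, with details of study drug administration (Protocol 8.4.2).

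What remains is that the stated rule has no worsening clause, and subject listings do not correct the period tables.

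**Conclusion.** The point holds in limited form. The period rule uses onset alone, and neither document counts an AE in a later period when it worsens or becomes serious on or after that period's injection. Unless sites opened a new record, worsening after a placebo subject's first LOR exposure is missing from the post-crossover period. If a single record carries the worst grade and is tabulated without a cut-off at the injection, the same event is also shown as severe or serious under placebo. That second consequence is conditional on a convention the documents do not give. The size is unknown, and so is the net direction between arms in period 1. The point is still worth acting on, because it bears on the first safety endpoint and on the stated purpose of the crossover, and a better rule is cheap.

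**What to change.** In SAP 10.1:

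1. Count an AE in a period if it starts, increases in severity or becomes serious on or after that period's injection and before the next one. The change takes effect at the second and third injections; the first period's open lower bound need not be narrowed.
2. Limit the highest-degree summary to values reached within the period being tabulated.
3. State how sites recorded a worsening of an open AE.
4. Use dated sources where they exist, such as SAE reports for seriousness. Where grade changes were not dated, list by original arm every AE that started before the second injection and was ongoing at it, with final severity and seriousness. The onset and resolution dates needed to select these events are already collected.

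No change to data entry is proposed. The SAP was approved in November 2023, after the decision to terminate (SAP 4.1), so a new eCRF instruction would come too late for most records.

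The cost is one derivation, one listing and a short addition to the text. An event that worsens will appear in more than one period, so event counts will no longer add up across periods, and a footnote should say so. Dating of severity changes will stay incomplete, and the listing shows that gap without closing it.

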10.2 Clinical Laboratory Evaluations

All chemistry, hematology and urinalysis results from the central laboratory will be summarized into shift tables as normal, non-clinically significant abnormal, and clinically significant abnormal. Assessments of clinical significance for abnormal values were made by the investigator on results that were outside of the normal range. Shift tables will compare the number and percent of assessments from each visit to baseline values for each treatment group.

All chemistry and hematology results from the central laboratory will be summarized for each treatment group. Descriptive statistics of each laboratory test at all timepoints will be provided along with the change from baseline at each subsequent visit. If a result is below the limit of quantification, it will be set to half the value for analysis (e.g., “< 3” will be analyzed as 1.5). The International System of Units (SI) will be used for all summaries.

Abnormal chemistry, hematology, urinalysis, and urine microscopy results for each subject will be provided in listings that will include laboratory test name, result, normal range, and an explanation for clinically significant values.

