3.2.3 Safety Endpoints

1. Adverse events (AEs) and serious adverse events (SAEs) (incidence, severity, and relationship to study drug) over the course of the study up to the end of the single-blind and placebo-controlled portion of the trial (i.e., prior to Second OA-07 injection [Lorecivivint only])
2. Clinically significant changes from parent-study-baseline clinical laboratory measures and vital signs, as assessed by the Investigator, over the course of the study up to Visit 3E (Week 48)

3. Change in serum bone biomarkers (N-terminal propeptides of procollagen type I [P1NP] and β -C-terminal telopeptide [β -CTX]) from parent-study baseline, and change in a serum cartilage biomarker (cartilage oligomeric matrix protein [COMP]) from parent-study baseline at Visit 3E (Week 48)

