7.4.3 Clinical Laboratory Evaluations

Specimens for clinical laboratory analysis were to be collected at Visit 2E, Visit 3E, every 52 weeks thereafter (e.g., Visits 6E, 8E, etc.), and at the Termination Visit. Subjects were asked to fast prior to the Visit 3E clinical laboratory collection. At a minimum, the following tests were conducted:

- **Chemistry panel:** Albumin, alkaline phosphatase (ALP), alanine aminotransferase (ALT), aspartate aminotransferase (AST), blood urea nitrogen, bicarbonate, calcium, calcium (corrected total), chloride, creatinine, glucose, lactate dehydrogenase (LDH), potassium, sodium, bilirubin (total)
- **Hematology:** Hemoglobin, hematocrit, red blood cell (RBC) count, white blood cell (WBC) count with differential, and platelet count
- **Urinalysis:** Clarity, specific gravity, pH, protein, glucose, ketones, nitrite, leukocyte esterase, and occult blood

Urine microscopy was to be performed if urinalysis urine protein, leukocyte esterase (WBC esterase), occult blood, or nitrite values were out of range, or if the Investigator deemed that the microscopy was clinically warranted.

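### The laboratory shift tables pool low and high abnormal results, so they cannot show the direction of a shift and dilute a one-sided tail change (minor, cheap to improve)

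*SAP*

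**What the plan says.** SAP 10.2 covers chemistry, hematology and urinalysis. Central laboratory results are "summarized into shift tables as normal, non-clinically significant abnormal, and clinically significant abnormal". The grading rule is: "Assessments of clinical significance for abnormal values were made by the investigator on results that were outside of the normal range". A result can be outside the range on either side, and neither document separates the two sides in these tables. The layout is: "Shift tables will compare the number and percent of assessments from each visit to baseline values for each treatment group".

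The same section plans two other outputs:

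- For chemistry and hematology, but not urinalysis: "Descriptive statistics of each laboratory test at all timepoints will be provided along with the change from baseline at each subsequent visit". SAP 7.1 includes the median, minimum and maximum among the descriptive statistics.
- Abnormal results from every panel are to be "provided in listings that will include laboratory test name, result, normal range, and an explanation for clinically significant values".

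The endpoint served, in SAP 3.2.3, is "Clinically significant changes from parent-study-baseline clinical laboratory measures and vital signs, as assessed by the Investigator". Protocol 7.2.1 asks that a laboratory result both out of range and judged clinically significant be reported as an adverse event. SAP 10.1 tabulates adverse events by system organ class and preferred term. SAP 10 plans no formal safety tests.

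**The concern.** A shift table is meant to show how many subjects crossed a laboratory limit and which way they went. The panel in SAP 7.4.3 includes tests for which low and high values mean different things: platelets, white cells and differential, hemoglobin, potassium, sodium, calcium and glucose. With low and high in one class, a reader who sees more abnormal platelet counts on LOR cannot tell from the table whether platelets fell or rose. A rise in low results must also stand out against the background of low and high results together.

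The gap is widest for NCS results. They generate no adverse event under Protocol 7.2.1, so among the planned by-arm counts they appear only in the shift table, without direction. Repeated dosing makes this worth attention: Protocol 2.1 gives long-term safety of repeated injections as a reason for the study, and Protocol 2.3.3 says that no completed study had examined repeated injections when it was written. With no safety tests planned, the reading depends on how clear the descriptive tables are.

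**Working it through.** The plan gives no figure on this point, so there is none to reproduce.

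**Step 1. Which planned outputs carry direction**

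| Output | By arm? | Direction? | Coverage |
|---|---|---|---|
| Shift table (SAP 10.2) | yes, counts | no | all three panels |
| Descriptive statistics and change (SAP 10.2, 7.1) | yes, no counts | yes | chemistry, hematology |
| Listings of abnormal results (SAP 10.2) | no, subject level | yes | all panels |
| AE tables (Protocol 7.2.1, SAP 10.1) | yes, counts | if the AE term carries it | CS results only |

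No row gives a by-arm directional count of NCS results. Urinalysis has no directional group summary except through AE terms for CS results.

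**Step 2. Tail change: a minority falls to low**

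Inputs:

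- n = 250 per arm. This is an assumption: SAP 5 says up to approximately 500, and the documents give no allocation ratio.
- The normal range covers the central 95%, with 2.5% on each side (assumption).
- 5% of LOR subjects, whatever their starting value, fall to low and the rest do not move (assumption).

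The index of visibility is the power that a 5% two-sided comparison would have. It is a yardstick, not a planned test: Φ(d/SE − 1.96), with SE = √{[p₀(1 − p₀) + p₁(1 − p₁)]/n}.

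- Low: p₀ = 0.025 and p₁ = 0.05 + 0.95 × 0.025 = 0.0738, so d = 0.0488. SE = √[(0.0244 + 0.0683)/250] = 0.0193. Index = Φ(2.53 − 1.96) = 72%.
- Merged abnormal: p₀ = 0.05 and p₁ = 0.05 + 0.95 × 0.05 = 0.0975, so d = 0.0475. SE = √[(0.0475 + 0.0880)/250] = 0.0233. Index = Φ(2.04 − 1.96) = 53%.

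The two differences are nearly equal (4.9 and 4.8 points), so there is almost no cancellation. The loss comes from the larger background rate. At 150 per arm the indices are 50% and 35%.

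**Step 3. Uniform shift of the whole distribution**

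Here the merged class does cancel. For a downward shift of δ SD, low = Φ(−1.96 + δ) and high = Φ(−1.96 − δ).

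- δ = 0.5: low goes from 2.5% to 7.2%, high from 2.5% to 0.7%, merged from 5.0% to 7.9%. Index 69% for low, 26% for merged.
- δ = 0.3: index 29% for low, 7% for merged.

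The planned mean change shows the same shift with its sign. Take an SD of change of 1, which follows from SD 1 at each visit and a correlation of 0.5. The index is then Φ(δ√(250/2) − 1.96). For δ = 0.3 it is Φ(3.35 − 1.96) = 92%; for δ = 0.5 it is Φ(5.59 − 1.96), over 99.9%.

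**Step 4. Low-to-high moves**

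A move from low to high with the same grade at both times falls on the diagonal. With bivariate normal values, correlation 0.5 to 0.7 and an upward shift of 0.5 SD, such moves occur in at most about 3.5 per 100,000 subjects. In 500 subjects that is 500 × 0.000035 = 0.02 expected per test and visit.

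**The case against.** The strongest reply is that the table fits its endpoint. The endpoint is change that the investigator judges clinically significant, and normal, NCS and CS are that scale. A low/normal/high layout is another common format, and no test or conclusion depends on the choice. This stands as a reason to keep the grading, but it is no reason to drop direction: the five-class table keeps the grades and collapses back to the planned three.

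A reader might infer three stronger points that the documents do not support:

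- That this is the only categorical summary of laboratory safety. CS results also reach the AE preferred-term tables (Protocol 7.2.1, SAP 10.1).
- That a one-directional drug effect would be largely cancelled and so missed. Heavy cancellation needs the whole distribution to move, and the planned mean changes would show that with its sign. When only a tail moves, the effect is dilution.
- That a low-to-high change tabulated as no shift is a practical problem. It needs the same grade at both times, and step 4 puts its frequency near zero.

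It also stands that minima, maxima and listings show extreme values with direction. They do not give counts by arm, and a reviewer would have to tally the listings by hand. For tests where low values rarely matter, such as ALT, AST and bilirubin, the split adds little.

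**Conclusion.** The point holds as a minor weakness of safety reporting. The shift tables pool low and high results within the NCS and CS classes. For tests with two-sided limits they cannot show direction, and they make a one-sided tail change less visible: 72% against 53% on the index in step 2. That size rests on the assumed 250 per arm, the assumed central-95% range and the assumed 5% of subjects falling to low, none of which the documents give. Data capture and the efficacy analyses are unaffected. What the report lacks is a directional count by arm, chiefly for NCS-low and NCS-high results, and a directional group summary for numeric urinalysis items.

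**What to change.** In SAP 10.2, build the chemistry and hematology shift tables with five classes: CS low, NCS low, normal, NCS high and CS high. The result and normal range needed are already held for the listings. Do the same for the numeric urinalysis items, pH and specific gravity, where the laboratory reports limits on both sides; the documents do not give the ranges. Keep three classes for the remaining urinalysis items.

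The cost is table-shell and programming work, with no new data. The downside is wider tables with some sparse cells.
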